17). The cognitive therapy component identifies negative sleep talk such as “I can’t stand it that I’m not getting to sleep” or “If I don’t get 8 hours of sleep tonight, I’ll do poorly at work and I could get fired”. Some cognitive therapists have a didactic focus. Others use a variety of cognitive restructuring procedures. While the therapies differ in approach, all are based on the observation that persons with insomnia have negative thoughts and beliefs about their condition and its consequences (Perlis, p. 18). Relaxation therapy focuses on managing stress, muscle relaxation and bedtime rituals that facilitate calming [<https://stanfordhealthcare.org/medical-treatments/c/cognitive-behavioral-therapy-insomnia.html>].

EFFECTIVENESS OF CBT-I:

The results using CBT-I among subjects with primary insomnia reporting sleep onset problems have been moderately effective for treating sleep onset problems. In a meta-analysis of 37 studies, Wu, Appleman, Salazar and Ong (2015) reported 36% of CBT-I patients were in remission from insomnia and no longer met diagnostic criteria for Insomnia Disorder at post-treatment evaluation compared to 16.9% in comparison conditions.

Key quantitative measures include sleep latency, the amount of time it takes person to initiate sleep upon retiring to bed; wake time after sleep onset (WASO); total sleep time (TST); and sleep efficiency, the percentage of sleep period during which person is actually asleep. In their review of the results of five randomized clinical trials which compared CBT-I to medications among patients with primary insomnia, Mitchell, Gehman, Perlis and Umscheid (2012) report sleep efficiency improved 8 to 16 percent with CBT-I. CBT-I generally led to improvement of 30 to 45 minutes in sleep latency and 30 to 60 minutes in total sleep time. Note that TST is not only an outcome variable but is manipulated as part of CBT-I using the restriction of time spent in bed. Sleep restriction therapy requires that time in bed be reduced to a time interval equal to the patient’s ‘sleep ability’ by measuring average TST with a sleep log during a baseline period. As noted by Mitchell, Gehrmann, Perlis and Umscheid, “The net result of this, after completion of CBT-I, is that many patients do not recover their baseline TST but are nevertheless substantially improved with respect to other aspects of sleep” (p. 6).

LIMITATIONS OF COGNITIVE BEHAVIOR THERAPY FOR INSOMNIA:

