There will be no statistically significant overall post-treatment minus pre-treatment differences across the four treatment groups in subjective sleep measures using standardized sum scores across the four measures of self-report data from Weekly Sleep Log. If ANOVA indicates a significant overall difference, pairwise t-tests will test the following hypotheses:

Hypothesis 1a. There will be no statistically significant post-treatment minus pre-treatment mean differences across the four treatment groups in the mean number of minutes to initiate sleep (SL);

Hypothesis 1b. There will be no statistically significant post-treatment minus pre-treatment differences across the four treatment groups in the mean number of minutes to return to sleep upon awakening after sleep onset (WASO);

Hypothesis 1c. There will be no statistically significant post-treatment differences across the four treatment groups in the mean total number of minutes of sleep (TST);

Hypothesis 1d. There will be no statistically significant post-treatment minus pre-treatment differences across the four treatment groups in the mean total number of minutes of sleep divided by the total number of minutes in bed (SE).

Hypothesis 2: Treatment Effect on Objective Measures of Sleep

There will be no statistically significant overall post-treatment minus pre-treatment differences across the four treatment groups in overall objective sleep measures using standardized sum scores for data from subjects wearing an ActiWatch 2. If ANOVA indicates a significant overall difference, pairwise t-tests will test the following hypotheses:

Hypothesis 2a. There will be no statistically significant post-treatment minus pre-treatment mean differences across the four treatment groups in the mean number of minutes to initiate sleep (SL);

Hypothesis 2b. There will be no statistically significant post-treatment minus pre-treatment differences across the four treatment groups in the mean number of minutes to return to sleep upon awakening after sleep onset (WASO);

Hypothesis 2c. There will be no statistically significant post-treatment minus pre-treatment differences across the four treatment groups in the mean total number of minutes of sleep (TST);

Hypothesis 2d. There will be no statistically significant post-treatment minus pre-treatment differences across the four treatment groups in the mean total number of minutes of sleep divided by the total number of minutes in bed (SE).

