There will be no statistically significant post-treatment minus pre-treatment mean differences across the four treatment groups in self report of extent of distress with sleep difficulty.

Hypothesis 7: Treatment Effect on Subjective Report of Impairment

There will be no statistically significant overall post-treatment minus pre-treatment differences across the four treatment groups in overall self-report of impairment due to sleep difficulty measures using standardized sum scores across the three measures. If ANOVA indicates a significant overall difference, pairwise t-tests will test the following hypotheses:

Hypothesis 7a. There will be no statistically significant post-treatment minus pre-treatment mean differences across the four treatment groups in self report of extent of social impairment due to sleep difficulty;

Hypothesis 7b. There will be no statistically significant post-treatment minus pre-treatment mean differences across the four treatment groups in self report of extent of occupational impairment due to sleep difficulty;

Hypothesis 7c. There will be no statistically significant post-treatment minus pre-treatment mean differences across the four treatment groups in self report of extent of academic impairment due to sleep difficulty.

Hypothesis 8: Endurance of Treatment Effect on Subjective Measures from Weekly Sleep Log

There will be no statistically significant overall 12 month follow up minus pre-treatment differences across the four treatment groups in subjective sleep measures using standardized sum scores across the four measures of self-report data from Weekly Sleep Log. If ANOVA indicates a significant overall difference, pairwise t-tests will test the following hypotheses:

Hypothesis 8a. There will be no statistically significant 12 month follow up minus pre-treatment mean differences across the four treatment groups in the mean number of minutes to initiate sleep (SL);

Hypothesis 8b. There will be no statistically significant 12 month follow up minus pre-treatment differences across the four treatment groups in the mean number of minutes to return to sleep upon awakening after sleep onset (WASO);

Hypothesis 8c. There will be no statistically significant 12 month follow up minus pre-treatment differences across the four treatment groups in the mean total number of minutes of sleep (TST);

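### Hypothesis 1c is worded as a post-treatment-only comparison of total sleep time, against the change-from-pre-treatment contrast in H1, its other sub-tests, H2c, H8c and the planned ANOVA: a minor contradiction to correct

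*Protocol*

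**What the plan says.** Under Hypotheses in Section 8.0, H1 is an omnibus test of the Weekly Sleep Log measures: "There will be no statistically significant overall post-treatment minus pre-treatment differences across the four treatment groups in subjective sleep measures using standardized sum scores". If the ANOVA is significant, four sub-hypotheses follow by pairwise t-tests. Three are changes from pre-treatment: sleep latency in H1a ("post-treatment minus pre-treatment mean differences across the four treatment groups in the mean number of minutes to initiate sleep (SL"), wake after sleep onset in H1b ("Hypothesis 1b. There will be no statistically significant post-treatment minus pre-treatment differences across the four treatment groups") and sleep efficiency in H1d ("Hypothesis 1d. There will be no statistically significant post-treatment minus pre-treatment differences across the four treatment groups"). H1c, on total sleep time (TST), reads "There will be no statistically significant post-treatment differences across the four treatment groups in the mean total number of minutes of sleep (TST" and subtracts nothing.

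The same quantity measured by ActiWatch is tested as a change: "Hypothesis 2c. There will be no statistically significant post-treatment minus pre-treatment differences across the four treatment groups". So is sleep-log TST at 12 months: "Hypothesis 8c. There will be no statistically significant 12 month follow up minus pre-treatment differences across the four treatment groups". The Statistics subsection of Section 8.0 assigns H1 to H3 to a 2 x 4 repeated measures ANOVA with pairwise t-tests after a significant result. The protocol gives no reason for treating TST differently in H1c.

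**The concern.** A hypothesis statement of this kind defines a test. As worded, the gate and one of the tests behind it use different contrasts: H1 asks whether the arms differ in change on a score that includes TST, and H1c then asks whether they differ in TST level after treatment. An analyst can follow H1c to the letter, or follow H1 and the Statistics subsection. The two routes use different data and can give different p-values. Because the trial is open label, the choice could be made with the results by arm in view. A statistical analysis plan may settle the matter, but the contradiction lies in a contrast that the protocol itself has fixed.

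**Working it through.** The plan states no figure on this point, so there is none to reproduce. The check is a comparison of wording, followed by a sizing of the consequence.

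**1. Wording side by side (Section 8.0)**

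| Hypothesis | Measure | Contrast as worded |
|---|---|---|
| H1 (gate) | four log measures, standardised sum | post minus pre |
| H1a | log sleep latency | post minus pre |
| H1b | log wake after sleep onset | post minus pre |
| **H1c** | **log TST** | **post only** |
| H1d | log sleep efficiency | post minus pre |
| H2c | ActiWatch TST | post minus pre |
| H8c | log TST at 12 months | 12 months minus pre |

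H1 to H7 with their sub-hypotheses make 5 + 5 + 1 + 1 + 6 + 1 + 4 = 23 statements. H1c is the only one of the 23 that does not subtract pre-treatment.

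**2. Fit with the planned test.** I read 2 x 4 as two times by four groups. With two times, the group-by-time interaction is the comparison of the four mean changes. A post-only contrast has one time point and does not fit that design.

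**3. What each contrast estimates.** Let δ be the true difference between two arms after treatment. The post-only contrast has expectation δ. The change contrast has expectation δ minus the expected baseline difference, which is 0 under the 1:1:1:1 randomisation in Section 2.0. Both estimate δ without bias.

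**4. Precision.** Assume equal pre and post SD (set to 1) and pre-post correlation ρ; the protocol gives neither. The variances per participant are:
- post-only: 1
- change: 2(1 − ρ)
- adjusted for baseline, large sample: 1 − ρ²

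Power is for one pairwise comparison at 40 per arm (Section 9.7.1), with an assumed two-sided 0.05 level and an assumed difference of 0.5 SD.

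| ρ | variance: post | change | adjusted | power: post | change | adjusted |
|---|---|---|---|---|---|---|
| 0.3 | 1 | 1.40 | 0.91 | 0.61 | 0.47 | 0.65 |
| 0.5 | 1 | 1.00 | 0.75 | 0.61 | 0.61 | 0.73 |
| 0.7 | 1 | 0.60 | 0.51 | 0.61 | 0.82 | 0.88 |
| 0.8 | 1 | 0.40 | 0.36 | 0.61 | 0.94 | 0.96 |

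Change beats post-only exactly when 2(1 − ρ) < 1, that is when ρ > 0.5. Adjustment is never worse than either: 1 − ρ² ≤ 1, and 1 − ρ² = (1 − ρ)(1 + ρ) ≤ 2(1 − ρ). The variance ratios do not depend on the number per arm.

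**5. Chance imbalance.** At 40 per arm the baseline difference between two arms has SE √(2/40) = 0.224 SD, a 95% range of ±1.96 × 0.224 = ±0.44 SD. Given a realised imbalance b, post-only is shifted by ρb and change by −(1 − ρ)b. For b = 0.3 SD:

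| ρ | shift, post-only | shift, change | false-positive rate, post-only | false-positive rate, change |
|---|---|---|---|---|
| 0.3 | +0.09 | −0.21 | 0.0579 | 0.0743 |
| 0.5 | +0.15 | −0.15 | 0.0695 | 0.0695 |
| 0.7 | +0.21 | −0.09 | 0.0765 | 0.0627 |

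The rates are conditional on that imbalance at 40 per arm. They use critical value 1.96 × SD × √(2/40) for each contrast's own SD, and conditional SE √(1 − ρ²) × √(2/40). Which contrast is shifted more depends only on which side of 0.5 the correlation lies.

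**The case against.** The strongest reply is that this is a dropped phrase and the rest of the protocol already settles it. H1 opens with the change contrast for all four log measures together, H2c has the full wording for the same quantity, and the ANOVA needs two time points. That is the likeliest explanation, and a reader should not infer that a post-only analysis was chosen on purpose. The reply does not remove the contradiction, because the pairwise follow-up tests take their contrast from the sub-hypotheses, and H1c states one that differs from the others.

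A second reply is that a post-only comparison is legitimate in a randomised trial. This stands. It is unbiased, and below a correlation of 0.5 it is more precise than the change score. The case for the change wording is consistency, not superiority.

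A third is that little hangs on it. H1c is reached only if H1 is significant, and the measure named with the primary endpoint in Section 2.0 is the Self Report Sleep Measures, not log TST. This stands too, and it sets the severity.

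**Conclusion.** The contradiction is established by the wording alone and needs no assumption beyond reading 2 x 4 as times by groups. Its consequence is minor: one conditional sub-test with an ambiguous contrast. The sizes above rest on an assumed correlation, equal pre and post SD, and, for power, an assumed effect and significance level.

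Four stronger readings are tempting and are not supported:

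- **That H1c cannot be compared with H8c.** Under randomisation the level and change contrasts estimate the same kind of between-arm difference. Within this one trial, part of a gap between the two results could come from baseline imbalance, but that is a narrower statement.
- **That post-only is never the better choice.** This holds against baseline adjustment only. Against the change score it fails below a correlation of 0.5.
- **That only H1c takes in chance imbalance, by a worrying number of minutes.** The change score takes it in as well, with opposite sign. The protocol gives no SD for TST, and the gain of 30 to 60 minutes in its Introduction is an improvement with CBT-I reported in a review, not a between-arm effect planned for this trial.
- **That the Introduction makes the baseline reference especially important for TST**, where it reports that "many patients do not recover their baseline TST but are nevertheless substantially improved with respect to other aspects of sleep". That sentence describes patients after sleep restriction and does not bear on which between-arm contrast to test.

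**What to change.** In H1c, insert *minus pre-treatment* after *post-treatment*, so that it matches H1, H1a, H1b, H1d, H2c and, at 12 months, H8c, and fits the ANOVA in the Statistics subsection.

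Preferably, analyse H1c and its sibling tests with the matching pre-treatment value as a covariate. In large samples this is never less precise than either contrast, and it accounts for the baseline imbalance that each of them carries in part. It should be applied to all of the sibling tests, so that H1c does not again become an exception.

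The cost is one phrase, or one model specification for the covariate version. No new data are needed: Sections 9.1.3, 9.4.5 and 9.5.3.1 provide for the sleep log at intake, and H1d already requires pre-treatment TST. The downside of the plain change wording is somewhat lower precision than post-only if the correlation is below 0.5, for example variance 1.40 against 1 at a correlation of 0.3. The covariate version avoids this. Either correction should be made before outcome data by arm are examined.

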Hypothesis 8d. There will be no statistically significant 12 month follow up minus pre-treatment differences across the four treatment groups in the mean total number of minutes of sleep divided by the total number of minutes in bed (SE).

Hypothesis 9: Endurance of Treatment Effect on Objective Measures

There will be no statistically significant overall significant overall 12 month follow up minus pre-treatment differences across the four treatment groups in overall objective sleep measures using standardized sum scores for data from subjects wearing an ActiWatch 2.

If ANOVA indicates a significant overall difference, pairwise t-tests will test the following hypotheses:

Hypothesis 9a. There will be no statistically significant post-treatment minus pre-treatment differences across the four treatment groups in each of the following objective sleep measures using data from subjects wearing an ActiWatch 2:

Hypothesis 9b. There will be no statistically significant 12 month follow up minus pre-treatment mean differences across the four treatment groups in the mean number of minutes to initiate sleep (SL);

Hypothesis 9c. There will be no statistically significant 12 month follow up minus pre-treatment differences across the four treatment groups in the mean number of minutes to return to sleep upon awakening after sleep onset (WASO);

Hypothesis 9d. There will be no statistically significant 12 month follow up minus pre-treatment differences across the four treatment groups in the mean total number of minutes of sleep (TST);

Hypothesis 9e. There will be no statistically significant 12 month follow up minus pre-treatment differences across the four treatment groups in the mean total number of minutes of sleep divided by the total number of minutes in bed (SE).

Hypothesis 10: Endurance of Treatment Effect on Insomnia Severity

There will be no statistically significant 12 months follow up minus pre-treatment mean differences across the four treatment groups in insomnia severity as measured by the Insomnia Severity Index (ISI).

Hypothesis 11: Endurance of Treatment Effect on Insomnia Diagnosis

There will be no statistically significant chi square 12 month follow up minus pre-treatment mean differences across the four treatment groups in the percentage of subjects who meet DSM-5 criteria for 780.52 Insomnia Disorder across time (pre-treatment; post-treatment; 12 month follow-up).

Hypothesis 12: Endurance of Treatment Effect on Sleep Satisfaction Measures

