There will be no statistically significant overall 12 month follow up minus post-treatment differences across the four treatment groups in overall satisfaction/ dissatisfaction with sleep using standardized sum scores for data from subjects across the five likert scale measures of satisfaction/dissatisfaction on the Self Report Sleep Measures.

If ANOVA indicates a significant overall difference, pairwise t-tests will test the following hypotheses:

Hypothesis 12a. There will be no statistically significant 12 month follow up minus post-treatment mean differences across the four treatment groups in self report of extent of satisfaction or dissatisfaction with ability to get to sleep at bedtime;

Hypothesis 12b. There will be no statistically significant 12 month follow up minus post-treatment mean differences across the four treatment groups in self report of extent of satisfaction or dissatisfaction with frequency of awakenings after having initiated sleep;

Hypothesis 12c. There will be no statistically significant 12 month follow up minus post-treatment mean differences across the four treatment groups in self report of extent of satisfaction or dissatisfaction with ability to return to sleep after awakenings during the night;

Hypothesis 12d. There will be no statistically significant 12 month follow up minus post-treatment mean differences across the four treatment groups in self report of extent of satisfaction or dissatisfaction with average quantity of sleep;

Hypothesis 12e. There will be no statistically significant 12 month follow up minus post-treatment mean differences across the four treatment groups in self report of extent of satisfaction or dissatisfaction with overall quality of sleep.

Hypothesis 13: Endurance of Treatment Effect on Subjective Sleep Distress

There will be no statistically significant 12 month follow up minus post-treatment mean differences across the four treatment groups in self report of extent of distress with sleep difficulty.

Hypothesis 14: Endurance of Self Report Sleep Satisfaction Measures

There will be no statistically significant overall 12 month follow up minus post-treatment differences across the four treatment groups in overall satisfaction/ dissatisfaction with sleep using standardized sum scores for data from subjects across the five likert scale measures of satisfaction/dissatisfaction on the Self Report Sleep Measures.

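### H12 to H14 measure endurance from post-treatment, not pre-treatment, so 12-month benefit on SRSM satisfaction and distress is never tested; H14 duplicates H12, leaving impairment without a 12-month test

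*Protocol*

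**What the plan says.** All of this is in Protocol Section 8.0, Hypotheses.

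- **H8 (sleep log):** "There will be no statistically significant overall 12 month follow up minus pre-treatment differences across the four treatment groups in subjective sleep measures".
- **H9 (ActiWatch), overall test:** "12 month follow up minus pre-treatment differences across the four treatment groups in overall objective sleep measures". Sub-hypotheses 9b to 9e use the same contrast. 9a does not: "Hypothesis 9a. There will be no statistically significant post-treatment minus pre-treatment differences across the four treatment groups".
- **H10 (ISI):** "There will be no statistically significant 12 months follow up minus pre-treatment mean differences across the four treatment groups in insomnia severity".
- **H11 (diagnosis):** "There will be no statistically significant chi square 12 month follow up minus pre-treatment mean differences across the four treatment groups".
- **H12 (satisfaction):** "There will be no statistically significant overall 12 month follow up minus post-treatment differences across the four treatment groups". 12a to 12e and H13 (distress) also start from post-treatment.
- **H14:** headed "Hypothesis 14: Endurance of Self Report Sleep Satisfaction Measures". Its overall statement and 14a to 14e repeat H12 and 12a to 12e.

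H5 (satisfaction), H6 (distress) and H7 (impairment) compare post-treatment with pre-treatment. The Statistics paragraph of Section 8.0 assigns a 2 x 4 repeated measures ANOVA to these hypotheses, that is, two time points by four groups. The Synopsis (Primary Endpoint) and Section 8.0 (Primary Objective) both name the SRSM as the measure of improvement in insomnia. The satisfaction, distress and impairment items all belong to the SRSM (Appendix IX).

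**The concern.** One label covers two different quantities, and the protocol gives no reason for the change. The contrast from pre-treatment asks how much better a participant is at 12 months than at the start. The contrast from post-treatment asks how much has changed since treatment ended. Its starting point is itself an outcome of the randomized treatment and can differ by arm.

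Two things are at stake. First, long-term benefit is tested for the sleep log, ActiWatch, ISI and diagnosis, but not for any item of the instrument the protocol names for improvement. Second, a difference between arms in H12 or H13 shows which arm moved most after treatment, and a reader could take it to show which arm helped most at 12 months.

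The duplicate adds a gap. H14 sits where the 12-month test of impairment would be expected, so impairment has none.

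**Working it through.** **1. Order of the list.**

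| Outcome | Initial effect | 12-month hypothesis | 12-month contrast |
|---|---|---|---|
| Sleep log | H1 | H8 | 12 months minus pre |
| ActiWatch | H2 | H9 | 12 months minus pre (9a: post minus pre) |
| ISI | H3 | H10 | 12 months minus pre |
| Diagnosis | H4 | H11 | 12 months minus pre |
| Satisfaction | H5 | H12 | 12 months minus post |
| Distress | H6 | H13 | 12 months minus post |
| Impairment | H7 | none (H14 repeats H12) | none |

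The first six pairs run in step, so the seventh would be H7 with H14.

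**2. What each contrast measures.** Score gains so that higher is better, and take equal pre-treatment means by randomization. Let g be an arm's gain at post-treatment and r the share kept at 12 months.

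- 12 months minus pre = r × g
- 12 months minus post = (r − 1) × g

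The first equals (post minus pre) plus (12 months minus post). H5 and H12 each test one part; no hypothesis tests the sum. The second expression is 0 when r = 1, whatever g is, and also 0 when g = 0. A fully kept gain and no gain therefore have the same expected value in H12.

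**3. Number at 12 months.** Section 9.7.2 gives 80% retention to session 6 and 80% from there to the end of follow-up. With 40 per group, 40 × 0.80 × 0.80 = 25.6, which reproduces the stated 25 if that is read as per group. The checks below use 25 per arm, with 40 as the upper end.

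**4. Illustrative size.** The protocol gives no alpha, SD, effect size or relapse rate for these hypotheses. The assumptions are: two-sided alpha 0.05; SD 1 at each visit; correlation 0.5 between visits, so that a change score has variance 2 × (1 − 0.5) = 1; initial gains of 0.8, 1.0 and 1.2 SD in three arms and 0 in the fourth; r from 0.5 to 1.25; 4,000 simulated trials per row. The test is the four-arm ANOVA on change scores, which is equivalent to the time-by-group test.

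| n per arm | r | Never-effective arm best: minus post | Never-effective arm best: minus pre | ANOVA rejects: minus post | ANOVA rejects: minus pre |
|---|---|---|---|---|---|
| 25 | 0.50 | 90% | 0.4% | 45% | 44% |
| 25 | 0.75 | 61% | 0% | 14% | 82% |
| 25 | 1.00 | 26% | 0% | 5% | 98% |
| 25 | 1.25 | 4% | 0% | 14% | 99.8% |
| 40 | 0.50 | 96% | 0% | 65% | 66% |
| 40 | 0.75 | 71% | 0% | 19% | 96% |
| 40 | 1.00 | 25% | 0% | 5% | 99.9% |
| 40 | 1.25 | 3% | 0% | 20% | 100% |

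At r = 1 the four arms have the same expected change from post-treatment, so 25% or 26% is chance.

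**5. One pair.** With g = 1 SD against 0, r = 1 and 25 per arm, the post-treatment contrast has an expected difference of (1 − 1) × 1 = 0. The pre-treatment contrast has an expected difference of 1 SD and power of 0.94.

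**The case against.** Change since the end of treatment is a legitimate maintenance question, and endurance can reasonably mean that a gain is kept once treatment stops. H5 and H6 would show separately that an arm never improved. Read with H12 and H13, they separate initial effect from later loss. This stands, and it is the reason to keep the post-treatment contrast in a secondary place. It does not close the gap, because neither test addresses total 12-month benefit. The paired hypotheses can also rest on different participants: under Missing Data in Section 8.0, those without 12-month data are removed from the 12-month analyses. A non-significant H12 with about 25 per arm would not show that a gain was kept.

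Stronger readings are tempting, but the documents do not support them:

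- **That an ineffective arm will come out as the most enduring.** This requires the effective arms to lose part of their gain. The protocol gives no relapse figure, its nulls have no direction, and it defines no endurance score or ranking.
- **That H12 to H14 would contradict H8 to H10.** Those hypotheses concern different outcomes, so divergent results need not conflict.
- **That H8 to H11 form a uniform template.** 9a is an exception.
- **That the duplicate inflates false positives.** The same test on the same data returns the same p-value. The harm is the missing impairment test.

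**Conclusion.** The point holds in this form. The reference point for endurance changes within one list without explanation. As written, no hypothesis tests 12-month benefit against pre-treatment for SRSM satisfaction or distress, and impairment has no 12-month test at all. These conclusions come from the text and need no assumptions. No SAP was available, but the protocol itself fixes the contrast hypothesis by hypothesis.

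That the post-treatment contrast cannot separate a fully kept gain from no gain follows from the algebra, given equal pre-treatment means. The ranking problem is conditional: under the assumed effects with 25 per arm, the never-effective arm looks best in 90% of runs at half retention and 61% at three-quarters. With full retention the arms tie, and with further gain the ineffective arm tends to rank last. The percentages depend on the assumed effects, SD and correlation; the direction depends only on whether effective arms relapse, hold or improve. This should be corrected before analysis.

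**What to change.** - Restate H12 (with 12a to 12e) and H13 as 12-month follow-up minus pre-treatment, consistent with H8 and H10.
- Keep 12-month minus post-treatment as a secondary or descriptive measure of loss of gain, read alongside H5 and H6.
- Replace the duplicate H14 with the 12-month minus pre-treatment counterpart of H7 (impairment), including its three sub-hypotheses.
- Correct 9a, which carries a post-treatment contrast under an endurance heading.

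The cost is an amendment to the wording of these hypotheses. No new data are needed: Sections 9.5.3.1, 9.5.3.8 and 9.5.3.11 already schedule the SRSM at Visits 1, 8 and 11.
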